#### Surgical:

The Investigator must withdraw a subject intraoperative for the following reasons:

- A simple or radical laparoscopic nephrectomy or laparoscopic nephroureterectomy not completed;
- Conversion to an open procedure, unless directly related to transection of the RA/RV (subject will be followed for safety up to 30 days postop); or
- Use of robotic assistance during surgery.

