1.2 Study Design

This was a prospective, randomized, controlled, multi-center, open-label study that planned to collect and compare data from the surgeon's current SOC stapler (for RA/RV transection) and PVS. Prospective subjects were informed about the nature of the research, given the informed consent document (ICD) to read, and if the subject understood the consent, were asked to provide written consent.

2 Treatment Assignment

Subjects were assigned to either the surgeon's current SOC stapler or PVS. The ECHELON FLEX™ PVS with Advanced Placement Tip is a sterile, single use instrument that simultaneously cuts and staples tissue. There are four staggered rows of staples, two on either side of the cut line. The ECHELON FLEX™ PVS with Advanced Placement Tip and reloads have a staple line that is approximately 35 mm long and a cut line that is approximately 30 mm long. The shaft can rotate freely in both directions and an articulation mechanism enables the distal portion of the shaft to pivot to facilitate lateral access to the operative site. The powered vascular stapler has been cleared for marketing by the FDA and is CE marked which allows for commercial distribution in the European Union. The device was used in accordance with its product labeling and Instructions for Use.

3 Randomization and Blinding Procedures

Subjects were randomized to either the surgeon's current SOC stapler or PVS in a 1:1 ratio. Randomization could have occurred at any time prior to surgery up to transection of the vessel(s). Sites were instructed to wait until as close as possible to the actual time of vessel transection so as to minimize randomized drops within the study.

Randomization was accomplished through utilization of envelopes at the study site. Randomization envelopes were created according to the “Work Instructions for the Creation of Randomization Envelopes”, document number WE001625, based on a randomization schedule generated by the Ethicon Biostatistics group. The randomization schedule was generated using a validated program that incorporated variable block sizes, and treatment assignment was balanced within each study site. This was an open-label study and therefore no blinding procedures were required.

4 Interval Windows

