5.3 Secondary and Additional Endpoints

Key additional endpoints in this study include: Surgeon Task Load Index, adverse events, and device usability questionnaires.

6 Levels of Significance

Evaluation of the acceptance criterion for this study is being accomplished through estimation of a 95% confidence interval. No hypotheses are specified for this study and no p-values are being calculated, therefore no level of significance is specified. All estimation of additional endpoints will be performed using 95% confidence intervals.

7 Analysis Sets

There will be three analysis sets defined:

- The Full Analysis Set (FAS) will consist of all randomized subjects who had a procedure performed and provide data on the number of surgical interventions.
- The Per Protocol (PP) Analysis Set will consist of all subjects in the FAS who had no major protocol violations. Determination of major deviations are conducted by the study Medical Director, Clinical Operations Trial Leader, Franchise Clinical Study Lead, and Biostatistician. A major deviation is defined as: A departure from the study protocol that has the potential to affect the scientific validity of the study (including deviations that: a) impact the analysis of the primary endpoint, or b) are due to inappropriate enrollment of a subject that does not meet the inclusion/exclusion criteria) or the safety, rights and welfare of the enrolled subject.
- The Safety Analysis Set consists of all randomized subjects on whom a procedure is started.

The primary performance endpoint analysis will be performed on the Full Analysis Set and subjects will be classified according to their randomized treatment group. The primary performance endpoint analysis will also be performed on the PP set as a sensitivity analysis to the results on the FAS. The analysis of additional endpoints will also be performed on the Full Analysis Set. Analysis of the primary safety endpoint and adverse events summaries will be performed on the Safety Analysis Set.

8 Sample Size Justification

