Sponsor Assessment of Protocol Deviations [1]			
Minor	xx (xx.x%)	xx (xx.x%)	xx (xx.x%)
Major	xx (xx.x%)	xx (xx.x%)	xx (xx.x%)
Number (%) of Subjects With at Least 1 Protocol Deviation [2]	xx (xx.x%)	xx (xx.x%)	xx (xx.x%)

1. Denominator used is the total number of protocol deviations reported.
2. Denominator used is the total number of subjects in the column header.

Table 4
 Surgical Characteristics
 Full Analysis Set

Characteristics	Standard of Care Stapler (N = ##)	Powered Vascular Stapler (N = ##)	Overall (N = ##)
Type of Surgery			
Laparoscopic Nephrectomy	xx (xx.x%)	xx (xx.x%)	xx (xx.x%)
Laparoscopic Nephroureterectomy	xx (xx.x%)	xx (xx.x%)	xx (xx.x%)
Number of Renal Arteries Transected			
0	xx (xx.x%)	xx (xx.x%)	xx (xx.x%)
1	xx (xx.x%)	xx (xx.x%)	xx (xx.x%)
2	xx (xx.x%)	xx (xx.x%)	xx (xx.x%)
3	xx (xx.x%)	xx (xx.x%)	xx (xx.x%)
Number of Ports			
1	xx (xx.x%)	xx (xx.x%)	xx (xx.x%)
2	xx (xx.x%)	xx (xx.x%)	xx (xx.x%)
3	xx (xx.x%)	xx (xx.x%)	xx (xx.x%)
4	xx (xx.x%)	xx (xx.x%)	xx (xx.x%)
Number of Drains Placed Intraoperatively			
0	xx (xx.x%)	xx (xx.x%)	xx (xx.x%)
1	xx (xx.x%)	xx (xx.x%)	xx (xx.x%)
2	xx (xx.x%)	xx (xx.x%)	xx (xx.x%)
ASA Physical Status			
Class I	xx (xx.x%)	xx (xx.x%)	xx (xx.x%)
Class II	xx (xx.x%)	xx (xx.x%)	xx (xx.x%)
Class III	xx (xx.x%)	xx (xx.x%)	xx (xx.x%)

Table 4
 Surgical Characteristics
 Full Analysis Set

Characteristics	Standard of Care Stapler (N = ##)	Powered Vascular Stapler (N = ##)	Overall (N = ##)
Estimated Blood Loss (mL)			
n	xx	xx	xx
Mean	xx.x	xx.x	xx.x
Standard Deviation	x.xxx	x.xxx	x.xxx
Median	xx.x	xx.x	xx.x
Minimum, Maximum	xx.x, xx.x	xx.x, xx.x	xx.x, xx.x
Transfusion of Blood or Blood Product Required?			
Yes	xx (xx.x%)	xx (xx.x%)	xx (xx.x%)
No	xx (xx.x%)	xx (xx.x%)	xx (xx.x%)
Procedure Converted to Open?			
Yes	xx (xx.x%)	xx (xx.x%)	xx (xx.x%)
No	xx (xx.x%)	xx (xx.x%)	xx (xx.x%)
Procedure Duration (min)			
n	xx	xx	xx
Mean	xx.x	xx.x	xx.x
Standard Deviation	x.xxx	x.xxx	x.xxx
Median	xx.x	xx.x	xx.x
Minimum, Maximum	xx.x, xx.x	xx.x, xx.x	xx.x, xx.x
Drain Duration (nights)			
n	xx	xx	xx
Mean	xx.x	xx.x	xx.x
Standard Deviation	x.xxx	x.xxx	x.xxx
Median	xx.x	xx.x	xx.x
Minimum, Maximum	xx.x, xx.x	xx.x, xx.x	xx.x, xx.x

Programming Note: Chest tube duration is calculated from date of surgery to date of final chest tube removal

Table 5
 Tumor Assessment – Pathology Lab
 Full Analysis Set

Characteristics	Standard of Care Stapler (N = ##)	Powered Vascular Stapler (N = ##)	Overall (N = ##)

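### Conversion to open, transfusion and blood loss are summarised only on the Full Analysis Set, which can omit subjects converted before any stapler firing; repeat these rows on the Safety Set

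*SAP*

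**What the plan says.** **Where the outcomes are shown.** SAP Table 4 (Surgical Characteristics) is labelled Full Analysis Set. Among its rows are estimated blood loss, "Transfusion of Blood or Blood Product Required" and "Procedure Converted to Open". The text of SAP 10.3 names the FAS for demographics but names no population for surgical characteristics. Only the table header does.

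**The two sets.** SAP 7 defines the FAS as "all randomized subjects who had a procedure performed and provide data on the number of surgical interventions". The other set is wider: "The Safety Analysis Set consists of all randomized subjects on whom a procedure is started".

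**Withdrawal.** Under the surgical reasons in Protocol 4.4, the investigator must withdraw a subject intra-operatively if the laparoscopic procedure is not completed, if robotic assistance is used, or for this reason: "Conversion to an open procedure, unless directly related to transection of the RA/RV".

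**Timing of randomisation.** Protocol 4.1 and 4.7.3.1 place randomisation before the procedure. SAP 3 allows it at any point up to vessel transection and says that sites were told to leave it as late as they could, "so as to minimize randomized drops within the study".

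**Missing data.** SAP 10.6 uses observed data only, with no imputation.

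**The concern.** For a subject who is converted before any firing, the event being counted can also be the reason for leaving the table. The subject is lost from numerator and denominator together, and that subject's blood loss and any transfusion are lost too.

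These rows are the planned arm-level summary of conversion, blood loss and intra-operative transfusion that does not depend on whether the surgeon attributes the event to RA/RV transection. The trial is open-label and that attribution is a judgement. A harm summary that ignores attribution should therefore cover everyone in whom the operation was started.

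**Working it through.** **1. Can a subject be in the Safety Set and outside the FAS?**

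| Situation after randomisation | Withdrawn under Protocol 4.4? | Safety Set | FAS |
|---|---|---|---|
| Converted before any RA/RV firing, reason not directly related to transection | Yes | In | Not secured: there may be no intervention data |
| Converted after at least one firing, reason not directly related | Yes | In | In: intervention data exist |
| Converted for a reason directly related to RA/RV transection | No | In | Should be in |

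Withdrawal is not itself an FAS criterion, so the gap is the first row. The wording leaves that row open. SAP 7 does not say whether a converted case counts as a procedure performed. Protocol 7.3 uses the definite article for the procedure, which makes exclusion easier to read into it. Table 4 has a line for zero renal arteries transected, which may mean that some of these subjects are kept; it may equally describe a subject in whom only a vein was stapled.

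**2. Does another planned summary fill the gap?** The SAP Appendix says that its shells cover all summaries to be produced.

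- Safety Set shells (Tables 3, 7 and 12 to 18): none has a conversion or blood-loss row. Table 7 has a transfusion row, limited to post-operative bleeding related to the RA or RV.
- Table 1: withdrawn conversions, non-completions and robotic cases share one Surgical row.
- Listings 6 (Procedure Details) and 21 (Completion/Withdrawal): they cover all subjects, but they are listings, not summaries by arm.

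**3. Size.** The plan gives no figure for conversion, transfusion or blood loss. Its only precision figure is a margin of at most 2.9% at a 6% rate per firing with 300 firings. It reproduces (1.96 × √(0.06 × 0.94 / 300) = 2.69%; Clopper-Pearson half-width 2.86%) but does not enter this point. What follows is illustration.

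Assume 250 / 2 = 125 Safety Set subjects per arm, c conversions, and d of them outside the FAS.

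- Safety Set rate = c / 125
- Table 4 rate = (c − d) / (125 − d)

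| c | Safety Set | Table 4, d = 1 | d = 2 | d = 5 |
|---|---|---|---|---|
| 2 | 1.6% | 0.8% | 0.0% | – |
| 5 | 4.0% | 3.2% | 2.4% | 0.0% |
| 8 | 6.4% | 5.6% | 4.9% | 2.5% |

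The first exclusion lowers the rate by c/125 − (c − 1)/124 = (125 − c)/15,500. That is 0.79, 0.77 and 0.75 percentage points for c = 2, 5 and 8, or about 0.8.

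For blood loss, assume a mean of 150 mL in retained subjects and 500 to 1000 mL in excluded ones. Table 4 shows 150 mL. The Safety Set mean with d = 1 is (150 × 124 + 500)/125 = 152.8 mL, up to 156.8 mL. With d = 5 it is 164 to 184 mL.

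**The case against.** The strongest reply is that the gap is narrow and the data are not lost. Subjects converted after a firing have supplied intervention data and stay in the FAS. Conversions directly related to RA/RV transection are exempt from withdrawal. Late randomisation is meant to keep the interval at risk short. Table 1 shows the size of both sets and the Surgical discontinuations by arm, so any loss from the FAS is visible. Adverse events are recorded from first incision whatever their relationship (Protocol 9.1.1 and 9.2.1), bleeding is an anticipated term (Protocol Appendix I), and Tables 12, 13 and 18 summarise events on the Safety Set. Table 4 is descriptive and no acceptance criterion rests on it. Protocol 7.3 and SAP 7 also place additional endpoints on the FAS, so moving the rows would conflict with both.

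Most of this stands. It limits the size, and it is a reason to add a display and not to move one. It does not close the gap: adverse event tables do not give blood-loss volume, conversion or transfusion as such, and a pooled discontinuation count does not give a conversion rate.

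One further argument is weaker: that an event before firing cannot differ by arm because the stapler has not been used. The stapler is placed around the vessel before it is fired. Protocol 1.0 describes the device's tip and placement, and SAP Table 11 asks about placement and dissection around the vessel. A difference between arms before firing cannot be ruled out, though nothing in the documents shows one.

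**Conclusion.** The point holds in a limited form. Table 4 can understate conversion to open, and also blood loss and intra-operative transfusion if the omitted subjects bled more. The subjects at issue are those randomised and then converted before any RA/RV firing. No Safety Set table summarises conversion, blood loss, or intra-operative or all-cause transfusion by arm. The size is about 0.8 percentage points of the conversion rate per excluded converted subject, assuming 125 per arm. The number of such subjects cannot be known from the documents and is meant to be small.

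A reader might infer more, and the documents do not support it:

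- That every withdrawn conversion leaves the FAS. Withdrawal is not an FAS criterion. The cases above in which Table 4 falls to 0% need every conversion to precede firing and to be excluded, so they are extremes.
- That transfusion appears in no Safety Set table. Table 7 shows the post-operative, RA/RV-related part.
- That a difference between arms is being hidden. It is possible but not shown.
- That the primary performance endpoint is affected. This point concerns the Table 4 outcomes only.

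**What to change.** Keep Table 4 on the FAS, so that Protocol 7.3 and SAP 7 need no change. In SAP 10.3 and the shells, add a short table that repeats the estimated blood loss, transfusion and conversion rows on the Safety Analysis Set by randomised group, including subjects withdrawn in the operating room. Split the Surgical row of Table 1 into its three reasons from Protocol 4.4: not completed, converted, robotic assistance.

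**Cost.** One sentence in SAP 10.3, one small extra table whose denominators may differ slightly from Table 4, and additional lines in Table 1. Protocol 4.7.3.2 already lists the data for collection during the procedure. A new table goes beyond the examples of minor modification in SAP 10.1, so if the SAP is already signed, the change is best recorded as an amendment. The primary analysis and the sample size are unchanged.

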10.4 Primary Endpoint Analyses

For the primary performance endpoint, summary statistics and 95% confidence intervals will be provided for the number and frequency of interventions by randomized treatment group. An intervention is defined as any firing which required a hemostasis intervention.

To account for the potential dependence among firings within a subject, the 95% confidence interval within each treatment group will be estimated using a bootstrap approach. For each subject, the outcome of each firing will be represented by a vector of 0's (indicating no intervention needed) and 1's (indicating an intervention was needed). This vector will be re-sampled with replacement to generate a bootstrap sampled vector of observations for each subject. Then, the proportion of observations requiring intervention for each subject will be calculated from this bootstrap vector. After obtaining a sample proportion of firings requiring intervention for each subject, the mean of these sample proportions will be calculated across all subjects within that treatment group to provide an estimated sample proportion of firings requiring intervention based on 1 iteration of the bootstrap process. This process will then be repeated a minimum of 5000 times to generate a sampling distribution for the proportion of firings requiring intervention within each treatment group. The mean of this sampling distribution will be provided as the point estimate of the

proportion of firings requiring intervention for that treatment group and the 95% confidence interval will be estimated by the lower 0.025 and upper 0.975 percentiles of this sampling distribution.

The table below demonstrates 1 iteration of this bootstrap process within a treatment group.

Subject ID	Observed Data Vector	Bootstrap Sampled Vector	Bootstrap-Based Sample Proportion
1	(0, 0, 1, 0, 0)	(0, 1, 0, 1, 0)	0.40
2	(0, 0, 0)	(0, 0, 0)	0.0
3	(0, 1, 0, 0)	(1, 0, 0, 0)	0.25
4	(0, 0, 1, 0, 0)	(0, 0, 0, 0, 0)	0.0
5	(0, 0)	(0, 0)	0.0
...
...
125	(1, 0, 0, 1, 0)	(0, 1, 0, 0, 0)	0.20
Summary			Average of above proportions to get 1 observation in the sampling distribution of the proportion of firings requiring intervention.

The above re-sampling process will then be repeated a minimum of 5000 times to estimate the sampling distribution for each treatment group.

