For each of the 5000 iterations, the difference in bootstrap estimated sample proportions (PVS – SOC) will be calculated and these values will be used to estimate the sampling distribution of the difference between PVS and SOC in the proportion of firings requiring intervention. The mean of this sampling distribution will be provided as the point estimate for the difference of the proportion of firings requiring intervention between groups and the one-sided upper-tailed 95% confidence interval limit for the difference will be estimated by the upper 0.95 percentile of this sampling distribution.

A secondary estimate of the proportion of firings requiring intervention will be provided under the assumption of independence of firings within a subject. This will be performed based on the total number of firings and the percentage will be calculated as the number of firings requiring an intervention divided by the total number of firings. The following SAS code will be used to generate two-sided 95% confidence intervals for the individual treatment groups and a one-sided upper-tailed 95% confidence interval for the difference between groups:

```
proc sort data=hemo_interv;
  by TrtGroup descending event;
run;
```

```

*two-sided exact 95% confidence interval for within treatment summary;
proc freq data=hemo_interv order=data;
  tables TrtGroup*event/binomial riskdiff exact;
run;
*one-sided exact 95% confidence interval for between treatment summary;
proc freq data=hemo_interv order=data;
  tables TrtGroup*event/binomial riskdiff alpha=0.10;
  exact riskdiff;
run;

```

This code assumes that the dataset hemo_interv contains one record per firing, the variable ‘TrtGroup’ contains the identifier for randomized treatment group (the SOC group should be listed in the first row of the table), and the variable ‘event’ identifies an occurrence of the primary endpoint with a 1 and no occurrence of the primary endpoint with a 0. The resulting output in the Column 1 Risk Estimates table in the SAS Output Window provides the individual confidence intervals for each treatment group as well as the confidence interval for the difference between groups. The above approach utilizes the exact methodology of Clopper and Pearson for estimation of the confidence intervals within each group as well as the difference between groups.

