Tumor Stage, Confirmed by Pathology			
Stage 0	xx (xx.x%)	xx (xx.x%)	xx (xx.x%)
Stage IA	xx (xx.x%)	xx (xx.x%)	xx (xx.x%)
Stage IB	xx (xx.x%)	xx (xx.x%)	xx (xx.x%)
Stage IIA	xx (xx.x%)	xx (xx.x%)	xx (xx.x%)
Stage IIB	xx (xx.x%)	xx (xx.x%)	xx (xx.x%)
Stage IIIA	xx (xx.x%)	xx (xx.x%)	xx (xx.x%)
Stage IIIB	xx (xx.x%)	xx (xx.x%)	xx (xx.x%)
Stage IV	xx (xx.x%)	xx (xx.x%)	xx (xx.x%)
Maximum Tumor Diameter (cm)			
n	xx	xx	xx
Mean	xx.x	xx.x	xx.x
Standard Deviation	x.xxx	x.xxx	x.xxx
Median	xx.x	xx.x	xx.x
Minimum, Maximum	xx.x, xx.x	xx.x, xx.x	xx.x, xx.x
Maximum Tumor Depth (cm)			
n	xx	xx	xx
Mean	xx.x	xx.x	xx.x
Standard Deviation	x.xxx	x.xxx	x.xxx
Median	xx.x	xx.x	xx.x
Minimum, Maximum	xx.x, xx.x	xx.x, xx.x	xx.x, xx.x
Primary Tumor TNM Classification			
TX	xx (xx.x%)	xx (xx.x%)	xx (xx.x%)
T0	xx (xx.x%)	xx (xx.x%)	xx (xx.x%)
Tix	xx (xx.x%)	xx (xx.x%)	xx (xx.x%)
T1	xx (xx.x%)	xx (xx.x%)	xx (xx.x%)
T1a	xx (xx.x%)	xx (xx.x%)	xx (xx.x%)
T1b	xx (xx.x%)	xx (xx.x%)	xx (xx.x%)
T2	xx (xx.x%)	xx (xx.x%)	xx (xx.x%)
T3	xx (xx.x%)	xx (xx.x%)	xx (xx.x%)
T4	xx (xx.x%)	xx (xx.x%)	xx (xx.x%)

Table 5
 Tumor Assessment – Pathology Lab
 Full Analysis Set

Characteristics	Standard of Care Stapler (N = ##)	Powered Vascular Stapler (N = ##)	Overall (N = ##)
TNM Classification for Regional Lymph Node			
NX	xx (xx.x%)	xx (xx.x%)	xx (xx.x%)
N0	xx (xx.x%)	xx (xx.x%)	xx (xx.x%)
N1	xx (xx.x%)	xx (xx.x%)	xx (xx.x%)
N2	xx (xx.x%)	xx (xx.x%)	xx (xx.x%)
N3	xx (xx.x%)	xx (xx.x%)	xx (xx.x%)
Distant Metastasis Present?			
Yes	xx (xx.x%)	xx (xx.x%)	xx (xx.x%)
No	xx (xx.x%)	xx (xx.x%)	xx (xx.x%)
Tumor Confirmed by Pathology as Non-Small Cell Lung Cancer?			
Yes	xx (xx.x%)	xx (xx.x%)	xx (xx.x%)
No	xx (xx.x%)	xx (xx.x%)	xx (xx.x%)

Table 6
 Intra-Operative Interventions on Renal Artery or Renal Vein
 Full Analysis Set

Characteristics	Standard of Care Stapler (N = ##)	Powered Vascular Stapler (N = ##)	Overall (N = ##)
Total Number of Vessels Transected	xxx	xxx	xxx
Renal Artery	xxx	xxx	xxx
Renal Vein	xxx	xxx	xxx
Bootstrap Based Estimate of Number of Vessel Transections Requiring Intervention n (%)	xx (xx.x%)	xx (xx.x%)	xx (xx.x%)
Two-sided 95% Confidence Interval for Percent Difference (One-sided 95% CI Upper Limit) for Percent Requiring Transection [2]	xx.x%, xx.x%	xx.x%, xx.x%	xx.x%, xx.x%
	xx.x% (xx.x%)		
Independent Samples Estimate of Number of Vessel Transections Requiring Intervention [1] n (%)	xx (xx.x%)	xx (xx.x%)	xx (xx.x%)

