Two-sided 95% Confidence Interval for Percent Difference (One-sided 95% CI Upper Limit) for Percent Requiring Transection [2]	xx.x%, xx.x%	xx.x%, xx.x%	xx.x%, xx.x%
	xx.x% (xx.x%)		
Type of Intervention, n (%) [3]			
Additional Stapling	xx (xx.x%)	xx (xx.x%)	xx (xx.x%)
Over-sewing	xx (xx.x%)	xx (xx.x%)	xx (xx.x%)
Compression	xx (xx.x%)	xx (xx.x%)	xx (xx.x%)
Use of Suture	xx (xx.x%)	xx (xx.x%)	xx (xx.x%)
Sealant	xx (xx.x%)	xx (xx.x%)	xx (xx.x%)
Buttress	xx (xx.x%)	xx (xx.x%)	xx (xx.x%)
Use of Energy	xx (xx.x%)	xx (xx.x%)	xx (xx.x%)
Clip Placement	xx (xx.x%)	xx (xx.x%)	xx (xx.x%)
Blood Product Transfusion	xx (xx.x%)	xx (xx.x%)	xx (xx.x%)
Additional Surgical Procedure	xx (xx.x%)	xx (xx.x%)	xx (xx.x%)
Other Intervention	xx (xx.x%)	xx (xx.x%)	xx (xx.x%)
Intervention Category, n (%) [4]			
No Intervention	xx (xx.x%)	xx (xx.x%)	xx (xx.x%)
Hemostasis Controllable	xx (xx.x%)	xx (xx.x%)	xx (xx.x%)
Hemostasis Intervention	xx (xx.x%)	xx (xx.x%)	xx (xx.x%)

[1] Denominator for calculation of percentage is the total number of vessels transected in that group.

[2] Difference is calculated as Powered Vascular Stapler minus Standard of Care Stapler.

[3] Denominator for calculation of percentage is the total number of vessels requiring intervention in that group.

[4] Hemostasis Controllable includes additional stapling, over-sewing, compression, use of suture, sealant, buttress, use of energy, clip placement, or other intervention.
 Hemostasis Intervention includes blood product transfusion and additional surgical procedure.

Table 7
 Post-Operative Interventions or Procedures Related to Renal Artery or Renal Vein Bleeding
 Safety Set

Characteristics	Standard of Care Stapler (N = ##)	Powered Vascular Stapler (N = ##)	Overall (N = ##)
Number of Subjects Requiring Post-Operative Intervention Related to Renal Artery or Renal Vein Bleeding			
n (%) [1]	xx (xx.x%)	xx (xx.x%)	xx (xx.x%)
95% Confidence Interval for Percent	xx.x%, xx.x%	xx.x%, xx.x%	xx.x%, xx.x%
Type of Intervention, n (%) [2]			
Blood Product Transfusion	xx (xx.x%)	xx (xx.x%)	xx (xx.x%)
Additional Surgical Procedure	xx (xx.x%)	xx (xx.x%)	xx (xx.x%)
Other Intervention	xx (xx.x%)	xx (xx.x%)	xx (xx.x%)

[1] Denominator for calculation of percentage is the total number of subjects in that group.
 [2] Denominator for calculation of percentage is the total number of subjects requiring intervention in that group.

Table 8
 Device Usage Details
 Full Analysis Set

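### SAP Table 6 divides the secondary intervention rate by vessels transected where SAP 10.4 divides it by firings; separately, the bootstrap estimate is a subject mean, not the proportion of firings named in the 3% criterion

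*SAP*

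**What the plan says.** **Criterion.** Protocol 7.4 bases the primary performance summary on the total number of firings. Protocol 7.4 and SAP section 8 both set the 3% limit on the difference, PVS minus SOC, in the proportion of firings that need an intervention.

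**Secondary estimate, text.** SAP 10.4 says that "the percentage will be calculated as the number of firings requiring an intervention divided by the total number of firings". The SAS code for the intervals has the same unit: "This code assumes that the dataset hemo_interv contains one record per firing".

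**Secondary estimate, table shell.** Table 6 labels this row "Independent Samples Estimate of Number of Vessel Transections Requiring Intervention" and attaches footnote 1, which reads "Denominator for calculation of percentage is the total number of vessels transected in that group". Footnote 3, for the types of intervention, reads "Denominator for calculation of percentage is the total number of vessels requiring intervention in that group". The row for the between-arm comparison is labelled "Difference (One-sided 95% CI Upper Limit) for Percent Requiring Transection". The table counts vessels, split into artery and vein, but not firings.

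**Bootstrap estimate.** SAP 10.4 resamples each subject's own firings, takes that subject's proportion, and then "the mean of these sample proportions will be calculated across all subjects within that treatment group". The Table 6 row is labelled "Bootstrap Based Estimate of Number of Vessel Transections Requiring Intervention n", followed by a percentage, and carries no denominator footnote.

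**The concern.** A programmer has two instructions for one cell of the primary-endpoint table. No section says that a firing and a vessel are the same thing, and SAP 10.4 treats the vessel count as an additional summary. A percentage that follows footnote 1 would be printed above an interval computed from firing-level records, and a reader could not detect this because total firings are not shown.

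The second issue concerns what is estimated. A mean of subject proportions weights each subject equally, whereas a proportion of firings weights each firing equally. If the bootstrap limit is the one compared with 3%, the quantity judged need not be the one for which the limit was set. The bootstrap also produces a percentage and no count, so the n in its row is undefined.

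**Working it through.** **Inputs from the documents.** About 250 subjects randomised 1:1, so about 125 per arm; at least 300 firings per arm; 2 to 3 firings per subject; background rate 6%; 95% margin of error at most 2.9% per group (protocol 7.2, SAP section 8). The documents give no vessel count, so 2 vessels per subject (250 per arm) is an assumption.

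**1. The plan's own precision figure.** At 6% of 300 firings (18 events):
- Wald half-width: 1.96 × √(0.06 × 0.94 / 300) = 2.69%.
- Clopper-Pearson interval for 18/300: 3.59% to 9.32%; mean half-width 2.86%, which rounds to 2.9%.

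At 6% of 250 vessels (15 events) the half-widths are 2.94% (Wald) and 3.15% (Clopper-Pearson). The stated figure fits 300 firings and not 250 vessels.

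**2. Effect of the denominator on the secondary row.**

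| Reading | Calculation | Rate | 95% CI (Clopper-Pearson) |
|---|---|---|---|
| SAP 10.4 text and code | 18/300 firings | 6.0% | 3.6% to 9.3% |
| Footnote 1, events still counted as firings | 18/250 vessels | 7.2% | 4.3% to 11.1% |
| Row label taken literally, events on an assumed 12 vessels | 12/250 vessels | 4.8% | 2.5% to 8.2% |

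Taking the percentage from footnote 1 and the interval from the SAP code would print 7.2% with 3.6% to 9.3%. If each vessel takes exactly one firing, the three readings coincide.

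**3. Subject mean against proportion of firings.** Let a share q of subjects have 3 firings with risk p3 per firing, and the rest have 2 firings with risk p2.
- Subject mean: (1 − q)p2 + q·p3.
- Proportion of firings: [2(1 − q)p2 + 3q·p3] / (2 + q).
- Gap (proportion of firings minus subject mean): q(1 − q)(p3 − p2) / (2 + q).

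With an assumed p2 = 4% and p3 = 8%:

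| q | Subject mean | Proportion of firings | Gap (points) |
|---|---|---|---|
| 0.2 | 4.80% | 5.09% | 0.29 |
| 0.4 | 5.60% | 6.00% | 0.40 |
| 0.5 | 6.00% | 6.40% | 0.40 |
| 0.8 | 7.20% | 7.43% | 0.23 |

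The gap is zero when p2 = p3 and changes sign when the two risks are swapped. In the difference between arms it cancels if both arms share the pattern, is about 0.4 points if only one arm has it, and is about 0.8 points if the arms have opposite patterns: at q = 0.5, 6.4% − 5.6% = 0.8 against 6.0% − 6.0% = 0.

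The six mock subjects in SAP 10.4 also show that the estimators differ. Their observed vectors give a subject mean of (1/5 + 0/3 + 1/4 + 1/5 + 0/2 + 2/5)/6 = 17.5%, against 5/24 = 20.8% of firings. These are made-up data and say nothing about the size to expect.

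**4. What the bootstrap interval covers.** The SAP resamples firings within each subject and keeps the set of subjects fixed. Assume 75 subjects with 2 firings and 50 with 3 (300 firings), 6% risk, and independent firings.
- True variance of the subject mean: 0.0564 × (75/2 + 50/3) / 125² = 0.0564 × 54.17 / 15,625, so SE = 1.40 points.
- Expected variance from within-subject resampling, where a subject with n firings contributes p(1 − p)(n − 1)/n²: 0.0564 × (75/4 + 50 × 2/9) / 125² = 0.0564 × 29.86 / 15,625, so SE = 1.04 points.

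Within-subject resampling therefore gives too small a standard error even when firings are independent, because it leaves out variation between subjects.

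**The case against.** The strongest reply is that this is a wording fault in a table shell. The method text says firings throughout, the code fixes one record per firing, and SAP 10.4.1 also classifies each firing. The shells carry other uncorrected text, such as a chest tube note and a lung cancer row, so vessel transection is plausibly loose wording for a firing. SAP 10.1 lets footnotes be reworded without an amendment. Most of this stands: the mixed row is a possible outcome rather than the expected one. It still leaves two written instructions for one cell, and correcting them costs almost nothing.

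On the estimator, the subject mean is a declared choice, and the pooled rate with a limit for the difference is already reported as secondary. That is correct, and it limits this part to a mismatch with the criterion and an unstated decision rule.

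A reader might infer more than the documents support:
- *That the estimate judged against 3% is divided by vessels.* Footnote 1 is attached only to the independent-samples row; the bootstrap row has vessel wording but no stated denominator.
- *That the vessel denominator inflates the rate, or by a bounded amount.* This holds the numerator at firings. The row label also counts vessel transections, and then the rate can fall, as 12/250 shows.
- *That footnote 3 contradicts the text.* SAP 10.4 gives no denominator for intervention types, so this is a matter of consistency only.
- *That the bootstrap decides the criterion.* This is inferred from the pooled estimate being called secondary; the SAP never says so.

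**Conclusion.** The conflict between SAP 10.4 and Table 6 footnote 1 is certain from the text and affects the secondary row. Its numerical size is not known: 6.0% against 7.2% rests on an assumed 2 vessels per subject with events counted as firings. No direction of bias is claimed.

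The second point is smaller. The bootstrap estimates a different quantity from the one in the criterion whenever firing counts vary and are related to risk. Under an assumed 4% against 8% risk the gap is at most about 0.4 points in one arm and about 0.8 points in the difference if the arms have opposite patterns, against a limit of 3 points; it is zero if risk and firing count are unrelated. The SAP should say which estimate decides. The shortfall in the bootstrap standard error (1.04 against 1.40 points under the stated assumptions) is a reason not to keep within-subject resampling for the deciding interval.

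**What to change.** **Table 6, no amendment needed under SAP 10.1.** Use firings in the row labels and in footnote 1, and in footnote 3 for consistency. Relabel the comparison row as percent of firings requiring intervention. Add a row for total firings, and keep vessels transected as the separate tabulation that SAP 10.4 already plans. Report the bootstrap row as a percentage without n.

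**Deciding estimate, by SAP amendment.** State that the 3% criterion is judged on total events over total firings in each arm, with the interval from resampling whole subjects. This matches the criterion and still meets the SAP's aim of allowing for dependence within a subject. Keep the subject mean as a supportive estimate. Because the study is open-label and the SAP describes conduct in the past tense, fix the amendment before outcome data by arm are reviewed, so that the choice cannot follow the results.

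**Cost.** A little programming, one amendment, and probably a wider interval, in a study that SAP section 8 already calls underpowered for this criterion. Protocol 4.7.3.2 lists the number of renal arteries but no firing count, so confirm that the eCRF records firings individually.
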